8.2.5 Analyses of Patients Characteristics at Time of SU Initiation

This analysis will be provided in the FAS population.

All patients' characteristics collected at SU initiation will be analyzed using descriptive statistics overall and according to treatment received at time of study inclusion: patients included in the study at time of Sunitinib initiation (Prospective group/SU in first line at inclusion) vs. patients included in the study at time of Axitinib initiation (Retrospective / prospective group/AXI in 2nd line at inclusion).

Note: some baseline characteristics related to SU initiation will be limited because of a retrospective part of the data collection. Whereas other ones, identified previously, will also be explored if the baseline is the AXI initiation (i.e. if patient was included in the study at time of Axitinib initiation).

These descriptions will be provided in the overall FAS population in a first time. Then they will be repeated on the SU-AXI subgroup.

Additionally, MSKCC prognosis classification (good/intermediate/poor) at SU initiation will be analyzed in patients who had PD as best response to 2nd line treatment and that for all 2nd line treatments (mainly for Axitinib and Nivolumab).

8.2.6 Analyses of Patients Characteristics at Time of AXI Initiation

This analysis will be provided in the FAS population on the SU-AXI subgroup.

All patients' characteristics collected at AXI initiation will be analyzed using descriptive statistics overall and according to treatment received at time of study inclusion: patients included in the study at time of Sunitinib initiation (Prospective group/SU in first line at inclusion) vs. patients included in the study at time of Axitinib initiation (Retrospective / prospective group/AXI in 2nd line at inclusion).

Additionally, MSKCC prognosis classification (good/intermediate/poor) at AXI initiation will be analyzed in patients who had PD as best response to Axitinib in 2nd line treatment.

9 LIST OF TABLES AND TABLE SHELLS

List of Tables and Table Shells will be provided in separate documents.

10 REFERENCES

Not Applicable.

11 APPENDICES

11.1 APPENDIX 1: DATA DERIVATION DETAILS

A1.1 Definition and Use of Visit Windows in Reporting

Endpoint	Target Date	Target Day	Definition [Day window]
QoL	Baseline	1	Day-6 to Day 1
QoL	Month 1	30	Day 15 to Day 44
QoL	Month 2	60	Day 45 to Day 74
QoL	Month 3	90	Day 75 to Day 104
QoL	Month 4	120	Day 105 to Day 134
QoL	Month 5	150	Day 135 to Day 164
QoL	Month 6	180	Day 165 to Day 194

Day 1 corresponds to the Axitinib start date.

In case of multiple observations falling within a given window, the observations selected for analysis will be identified as follows:

- 1. The observation closest to the target day will be used.
- 2. If the observations are at equal distance from the target day in absolute value, the latest observation within the analysis window will be used.

A1.2 Further Definition of Endpoints

FKSI-19 questionnaire

NCCN-FACT FKSI-19

Below is a list of statements that other people with your illness have said are important. Please circle or mark one number per line to indicate your response as it applies to the past 7 days.

5 (a		Not at all	A little bit	Some- what	Quite a bit	Very much
GPI	I have a lack of energy	0	1	2	3	4
GP4	I have pain	0	1	2	3	4
C2	I am losing weight	0	1	2	3	4
HI7	I feel fatigued	0	1	2	3	4
Bl	I have been short of breath	0	1	2	3	4
BRM3	I am bothered by fevers (episodes of high body temperature)	0	1	2	3	4
BPI	I have bone pain	0	1	2	3	4
12	I have been coughing	0	1	2	3	4
HI12	I feel weak all over	0	1	2	3	4
RCC 2	I have had blood in my urine	0	1	2	3	4
C6	I have a good appetite	0	1	2	3	4
GF5	I am sleeping well	0	1	2	3	4
GE6	I worry that my condition will get worse	0	1	2	3	4
GP2	I have nausea	0	1	2	3	4
CS	I have diarrhea (diarrhoea)	0	1	2	3	4
GPS	I am bothered by side effects of treatment	0	1	2	3	4
GF1	I am able to work (include work at home)	0	1	2	3	4
GF3	I am able to enjoy life	0	1	2	3	4
GF7	I am content with the quality of my life right now	0	1	2	3	4

DRS-P=Disease-Related Symptoms Subscale – Physical DRS-E=Disease-Related Symptoms Subscale – Emotional TSE=Treatment Side Effects Subscale FWB=Function and Well-Being Subscale

CCL

FKSI-19 scoring guidelines

- 1. Record answers in "item response" column. If missing, mark with an X
- 2. Perform reversals as indicated, and sum individual items to obtain a score.
- 3. Multiply the sum of the item scores by the number of items in the subscale, and then divide by the number of items answered. This produces the symptom index score.
- 4. As with all FACIT questionnaires, a high score is good. Therefore, a score of "0" is a severely symptomatic patient and the highest possible score is an asymptomatic patient.

If >50% of items were completed, the FKSI scores were calculated as the sum of the item responses divided by the number of items completed multiplied by the total number of items in the scale (eg, 19 in the case of the FKSI-19). If fewer than 50% of the items were completed, the scores were considered missing.

Scale	Item Code	Reverse ite	em	Item response	Item Score
FKSI-19	GP1	4			=
Total	GP4	4			=
Score range: 0-76	C2	4			=
C	HI7	4			=
	B1	4			=
	BRM3	4			=
	BP1	4			=
	L2	4			=
	HI12	4			=
	RCC2	4			=
	C6	0	+		=
	GF5	0	+		=
	GE6	4			=
	GP2	4			=
	C5	4			=
	GP5	4			=
	GF1	0	+		=
	GF3	0	+		=
	GF7	0	+		=

Sum individual item scores:

Multiply by 19:

Divide by number of items answered: =FKSI-19

Subscale	Item Code		Reverse item	Item response	Item Score
FKSI-DRS-P	GP1	4	-		=
(Disease Related	GP4	4	-		=
Symptoms-Physical)	C2	4	-		=
Score range: 0-48	HI7	4	-		=
Score runge. 0-40	B1	4	-		=
	BRM3	4	-		=
	BP1	4	-		=
	L2	4	-		=
	HI12	4	-		=
	RCC2	4	-		=
	C6	0	+		=
	GF5	0	+		=
				Sum individual item scores Multiply by12:	s:

Divide by number of items answered: =FKSI-DRS-P

Subscale	Item Code	Reverse item	Item response	Item Score
FKSI-DRS-E				
(Disease Related				
Symptoms-Emotional)	GE6	4 -		= =FKSI-DRS-E
Score range: 0-4				

Subscale	Item Code	Reverse	item	Item response	Item Score
FKSI-TSE	GP2	4	-		=
(Treatment	C5	4	-		=
Side Effects)	GP5	4	-		=
Score range: 0-12					
				Sum individual item so	cores:
				Multiply	by 3:
			Divid	e by number of items answ	vered: =

Subscale	Item Code	Reverse item		Item response	Item Score
FKSI-F/WB	GF1	0	+		=
(Function/	GF3	0	+		=
Well-Being)	GF7	0	+		=
Score range: 0-12					
				Sum individual item score	25:

Sum individual item scores: _____

Multiply by 3: _____

Divide by number of items answered: =FKSI-F/WB

RE and MN domains of SF-36 questionnaire

INSTRUCTIONS: This set of questions asks for your views about your health. This information will help keep track of how you feel and how well you are able to do your usual activities. Answer every question by marking the answer as indicated. If you are unsure about how to answer a question please give the best answer you can.

- Items of Role-Emotional (RE) domains

5.	During the past 4 weeks , have you had any of the following problems with your work or other regular daily activities as a result of any emotional problems (e.g. feeling depressed or anxious)?						
	(Please circle one number on each line.)	Yes	No				
5(a)	Cut down on the amount of time you spent on work or other activities	1	2				
5(b)	Accomplished less than you would like	1	2				
5(c)	Didn't do work or other activities as carefully as usual	1	2				

- Items of Mental-Health (MH) domains

	(Please circle one number on each line.)	All of the Time	Most of the Time	A Good Bit of the Time	Some of the Time	A Little of the Time	None of the Time
9(b)	Have you been a very nervous person?	1	2	3	4	5	6
9(c)	Have you felt so down in the dumps that nothing could cheer you up?	1	2	3	4	5	6
9(d)	Have you felt calm and peaceful?	1	2	3	4	5	6
9(f)	Have you felt downhearted and blue?	1	2	3	4	5	6
9(h)	Have you been a happy person?	1	2	3	4	5	6

SF-36 scoring guidelines

Step 1: For ease of interpretation each scale is then transformed to a 0-100 scale (see table below). This transformation converts the lowest and highest possible scores to zero (poor quality of life) and 100 (best quality of life) respectively.

Items	Observed Score of items			
	Answer	(out of 100)		
5a, 5b et 5c	1	0		
	2	100		
9d, 9h	1	100		
	2	80		
	3	60		
	4	40		
	5	20		
	6	0		
9b, 9c, 9f	1	0		
	2	20		
	3	40		
	4	60		
	5	80		
	6	100		

Score of items for each item of RE and MH domains of SF-36 questionnaire

Step 2:

The score of Role-Emotional (RE) domain of SF-36 will be defined as the sum of scores of items 5a, 5b and 5c, divided by 3.

The score of Mental Health (MH) domain of SF-36 will be defined as the sum of scores of items 9b, 9c, 9d, 9f and 9h, divided by 5.

For each domain:

- if >50% of items were missing, the missing values will be replaced by the average score of other completed items,
- If fewer than 50% of the items were completed, the scores were considered missing.

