7 HANDLING OF MISSING VALUES

The majority of data will be collected with a website (except for FKSI-19 and SF-36 questionnaires). In this website, the input of certain data will be obligatory, limiting the number of missing values, particularly for endpoints.

Regarding the descriptive analyses of each variable, it will be based on the available data ("observed-case analysis"), considering missing data as non-informative. The number of missing data will be documented for each analysis.

The analysis of the primary endpoint is a survival analysis which is known to efficiently handle missing data: all patients are included in the analysis and missing data are called right-censored data.

For continuous endpoints (QoL endpoints), a mixed model for repeated measures (MMRM) will be used to analyse longitudinal data. Missing data will not be imputed. However, this analysis will be performed on all patients having a baseline value and at least one post-baseline value. The model will be valid under the assumption of data missing at random (MAR).

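### The two SF-36 missing-item rules order opposite actions for the same questionnaires, and neither covers RE with one item missing or MH with one or two missing

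*SAP*

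**What the plan says.** In SAP Appendix 1, A1.2 (SF-36 scoring guidelines), Step 1 puts every item on a 0 to 100 scale: "This transformation converts the lowest and highest possible scores to zero (poor quality of life) and 100 (best quality of life) respectively". Step 2 defines RE as "the sum of scores of items 5a, 5b and 5c, divided by 3" and MH as "the sum of scores of items 9b, 9c, 9d, 9f and 9h, divided by 5". SAP section 6.3.3 repeats both divisors.

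Two missing-item bullets then apply to each domain:

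- Bullet 1: "if >50% of items were missing, the missing values will be replaced by the average score of other completed items".
- Bullet 2: "If fewer than 50% of the items were completed, the scores were considered missing".

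The FKSI-19 guidelines in the same appendix prorate under the opposite condition: "If >50% of items were completed, the FKSI scores were calculated as the sum of the item responses divided by the number of items completed", rescaled to the full number of items. They then set the score to missing in the same terms as bullet 2.

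SAP section 7, in the paragraph on the mixed model for the QoL endpoints, states: "Missing data will not be imputed". It limits that analysis to patients with a baseline value and at least one later value.

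**The concern.** A questionnaire with more than half of its items missing is the same questionnaire as one with fewer than half completed. Bullet 1 tells the programmer to impute it and bullet 2 tells the programmer to discard it. A questionnaire with a few skipped items, where averaging the answered ones is easiest to defend, meets neither bullet.

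Skipped items are foreseeable. The questionnaires are on paper, filled in at home each month and posted back (protocol 8.2, SAP 2.1). SAP section 7 relies on obligatory web fields to limit missing data but excepts these questionnaires from web collection.

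The RE and MH scores and their changes from baseline feed the descriptive tables and the mixed models (SAP 8.1.4, 8.2.4), which serve a stated secondary objective. As written, the rule cannot be programmed without a choice that the plan does not make.

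**Working it through.** The plan gives no figure to reproduce, so the check runs every possible number of missing items through the two bullets and then sizes the consequences.

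**Inputs.** RE has k = 3 items and divisor 3; MH has k = 5 items and divisor 5; 0 is worst and 100 best; the two bullets are as quoted (all from SAP Appendix 1, A1.2).

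**Step 1: which bullet applies.** With m items missing, bullet 1 applies if m/k > 50% and bullet 2 if (k − m)/k < 50%.

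| Domain | Missing | % missing | Bullet 1 (impute) | Bullet 2 (set missing) |
|---|---|---|---|---|
| RE | 1 of 3 | 33% | no | no |
| RE | 2 of 3 | 67% | yes | yes |
| RE | 3 of 3 | 100% | yes | yes |
| MH | 1 of 5 | 20% | no | no |
| MH | 2 of 5 | 40% | no | no |
| MH | 3 of 5 | 60% | yes | yes |
| MH | 4 of 5 | 80% | yes | yes |
| MH | 5 of 5 | 100% | yes | yes |

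The bullets always apply together or not at all. With every item missing, bullet 1 also has nothing to average. Bullet 1 alone would score RE from one answer of three, and MH from one or two of five.

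**Step 2: test the inversion.** If bullet 1 is keyed to more than 50% completed, as for FKSI-19, then RE with 1 missing and MH with 1 or 2 missing are prorated, and the rest are set to missing. No overlap or gap remains, because exactly 50% cannot occur with 3 or 5 items.

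**Step 3: the uncovered cases under each possible handling.** Let b be the mean of the answered items.

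- *Strict sum.* An absent item leaves the sum undefined and the score is missing. If this happens at baseline, the patient leaves that domain's mixed model under the section 7 entry condition.
- *Proration.* The score is b. This is sensible, but the SF-36 text does not provide for it.
- *Skipped items summed as 0 over the fixed divisor* (an assumption; the SAP does not say this). The score is b(k − m)/k, a shortfall of b × m/k:

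| Case | Zero-filled score | Mean of answered | Difference |
|---|---|---|---|
| RE 100, 100, missing | 200/3 = 66.7 | 100 | −33.3 |
| RE 100, 0, missing | 100/3 = 33.3 | 50 | −16.7 |
| RE 0, 0, missing | 0 | 0 | 0 |
| MH 1 missing, rest 80 | 320/5 = 64 | 80 | −16 |
| MH 1 missing, rest 60 | 240/5 = 48 | 60 | −12 |
| MH 2 missing, rest 80 | 240/5 = 48 | 80 | −32 |

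**Step 4: direction in change scores, still under zero-fill.** Take a patient whose answered RE items are all 100 at both visits. One item skipped only at follow-up gives 66.7 − 100 = −33.3, an apparent deterioration. One skipped only at baseline gives 100 − 66.7 = +33.3, an apparent improvement. One skipped at both gives 0.

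**The case against.** The best defence is that this is a one-word slip with an obvious repair. The FKSI-19 rule in the same appendix shows what was meant, and a careful programmer would probably write missing for completed off as a drafting error. RE and MH are two of the seven QoL scores in SAP 8.2.4, and no primary endpoint is touched. All of that stands and limits the weight of the point. It does not remove it: nothing else in the SAP resolves the contradiction or fills the gap, and the choice should not be left to programming.

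A reader might also infer three stronger things that the documents do not support.

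- *Incomplete questionnaires will be scored too low.* This needs skipped items to count as 0, which the SAP never says. An undefined sum, and so no score, is at least as natural a reading. The observed-case approach in section 7 gives no support to assigning the worst value. Even with zero-fill there is no shortfall when every answered item scores 0.
- *Skipped items will look like deterioration.* Even with zero-fill, the sign of the error in a change score depends on which visit has the gap.
- *Near-empty questionnaires will be scored.* Bullet 1 would do so, but bullet 2 discards the same questionnaires. The defect is the conflict between them.

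The section 7 sentence on not imputing does not settle the matter either. It sits in the mixed-model paragraph and can be read as concerning missing visits, not missing items.

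**Conclusion.** The SF-36 missing-item rule is wrong as written. It contradicts itself for RE with 2 or 3 items missing and for MH with 3 to 5 missing, and it is silent for RE with 1 missing and MH with 1 or 2 missing. That follows from the text alone. That bullet 1 is inverted is an inference from the FKSI-19 rule, and a strong one, since the inversion explains both the overlap and the gap.

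The numerical effect is conditional. If an absent item voids the score, the cost is lost scores and, for a gap at baseline, a patient lost from that domain's model. If skipped items are summed as 0, one missing item distorts RE by 0 to 33 points, and MH by 16 points when the rest are at 80. These are errors in single questionnaires. The documents give no rate of item non-response, so no effect on a group mean can be stated. The point concerns secondary QoL endpoints only, but should be corrected before the scores are programmed.

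**What to change.** Replace the two SF-36 bullets in Appendix 1 with one rule, for example: *Where at least half of the items in a domain are answered, each unanswered item takes the mean of the answered items in that domain, so the domain score is that mean. Where fewer than half are answered, the domain score is missing.* In practice RE then needs two of its three items and MH three of its five.

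Add a sentence to SAP section 7 saying that this item-level rule is separate from the statement that missing data are not imputed, which would then concern domain scores missing at a visit.

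The cost is two sentences in the SAP and about one line of scoring code. No data collection changes.

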11.2 APPENDIX 2: ADDITIONAL STATISTICAL METHODOLOGY DETAILS

A2.1 Further Details of the Statistical Methods

Not Applicable.

PFIZER CONFIDENTIAL

Page 41 of 41
